#### **8.3.2.4 Expected Adverse Events**

##### ***Expected disease-related AEs***

Neuroendocrine tumour disease has a serious cluster of symptoms. Common disease-related events are:

- Gastrointestinal hormone disorders including potential symptoms, e.g. hypoglycaemia, hyperglycaemia, gastritis, steatorrhea, cholecystolithiasis, weight loss, anorexia
- Skin irritations and sore skin
- Obstructive symptoms and vomiting
- Diarrhoea
- Indigestion
- Abdominal pain or back pain
- Gastroesophageal reflux
- Nausea

##### ***Expected conduct-related AEs***

The use of an indwelling cannula for the purpose of blood sampling and administration of study drug may be accompanied by mild bruising and also, in rare cases, by transient inflammation of the vessel

wall. After initial irritation, the presence of an indwelling cannula is usually painless and hardly noticeable. The same applies to single vein punctures for blood sampling.

Patients may also experience discomfort from the imaging facilities, e.g. back pain, claustrophobia, headache, chill, and others.

***Expected AEs related to the nephroprotective amino acid solution***

Amino acid infusion may cause elevation of serum potassium levels by inducing a shift of potassium ions from cells to the extracellular department. This shift can lead to significant hyperkalemia in up to 19% of patients (Giovacchini et al., 2011), leading to malaise, palpitations, muscle weakness and mild hyperventilation. Generalised flushing, fever, nausea and vomiting have also been reported during infusions of amino acid solutions. Prevention and treatment of these symptoms are described in Sections 6.1.3 and 6.1.4.

***Expected AEs related to an investigational drug***

Please refer to the IB (Section 6.8.2 Undesirable Effects Related to Lu-edotreotide) for Lu-edotreotide.

Patients should be carefully monitored for side effects. Pre-existing co-morbidities (e.g. pre-existing nephropathy and diabetes mellitus) must be assessed and appropriate monitoring and prophylactic measures are to be applied according to local standard of care.

TLS was previously reported in patients receiving Lu PRRT. Patients should be monitored for the development of TLS or CRS. In case of suspected TLS or CRS development, Lu-edotreotide treatment must be discontinued and symptomatic treatment is to be given immediately according to local standard of care.

If hypersensitivity or anaphylactic reaction occurs, treatment with Lu-edotreotide must be discontinued and appropriate treatment is to be given according to local standard of care.

Please refer to the local product information for the countries participating in the study for everolimus.

***Expected Adverse Drug Reactions***

The definition below follows ICH-GCP (see also ICH Guideline for Clinical Safety Data Management: Definitions and Standards for Expedited Reporting):

***Adverse drug reaction (ADR)***

In the pre-approval clinical experience with a new medicinal product or its new usages, particularly as the therapeutic dose(s) may not be established, all noxious and unintended responses to a medicinal product related to any dose should be considered as ADR. The phrase “responses to a medicinal product” means that a causal relationship between a medicinal product and an AE is at least a reasonable possibility, i.e., the relationship cannot be ruled out.

Regarding marketed medicinal products: a response to a drug which is noxious and unintended and which occurs at doses normally used in man for prophylaxis, diagnosis, or therapy of diseases or for modification of physiological function.

### ***Unexpected Adverse Drug Reactions***

An unexpected adverse drug reaction is defined as any adverse drug experience, the nature, specificity or severity of which is not consistent with the applicable product information (e.g. investigator's brochure for an unapproved investigational product or Summary of Product Characteristics for an approved product). "Unexpected" as used in this definition refers to an adverse drug experience that has not been previously observed and included in the product information, rather than from the perspective of such experience not being anticipated from the pharmacological properties of the investigational product. Any unexpected adverse drug reaction, as of formal criteria of an SAE may not be met, (see above), has to be reported by the investigator immediately after informing the sponsor, using an SAE form.

### **8.3.2.5 Serious Adverse Events**

#### ***Definition of Serious Adverse Events***

##### Definition

The following SAE definition is based on ICH guidelines and the final rule issued by the FDA and effective 06-Apr-1998. It is to be applied to both, AEs (defined in Section 8.3.2.1) and baseline findings (defined in Section 8.3.1.1).

An SAE is classified as any untoward medical occurrence that at any dose

- Results in death, or
- Is life threatening, or
- Requires inpatient hospitalisation or prolongation of existing hospitalisation, or
- Results in persistent or significant disability / incapacity, or
- Is a congenital anomaly / birth defect, or
- Is a medically important event or reaction.

The term 'life threatening' in the definition refers to an event in which the patient was at risk of death at the time of the event, it does not refer to an event which hypothetically might have caused death if it were more severe.

Medical and scientific judgment should be exercised in deciding whether it is appropriate to report an AE as serious also in other situations, such as important medical events that may not be immediately life threatening or result in death or hospitalisation but may jeopardise the patient or may require intervention to prevent one of the other outcomes listed in the definition above. These should also usually be considered serious. Examples of such events are intensive treatment in an emergency room or at home for allergic bronchospasm; blood dyscrasias or convulsions that do not result in inpatient hospitalisation; or development of drug dependency or drug abuse.

### ***Actions and reporting obligations in case of serious adverse events***

All adverse events that meet the criteria for serious require the completion of a SAE Report Form, in addition to being recorded on the AE pages of the patients' CRF. This applies to all SAEs, whether or not they were considered to be related to study treatment.

**SAEs must be reported within 24 hours**, once the investigator or other study site personnel are aware of the event. An initial written report should be prepared using the SAE Report Form and sent to the sponsor preferably per email ([[contact]](mailto:[contact])) or (in case of email system failure) per fax ([contact]). This report should provide a detailed description of the SAE. Any other relevant documents such as anonymised copies of hospital records may also be attached, if available. If it is not possible to notify the sponsor by email or fax within 24 hours, an initial notification to your assigned clinical research associate (CRA) should be made by telephone, to include the following information:

- Identification of the investigator and centre
- Patient number
- Confirmation of study medication given, with date and dose
- Concomitant medication and indication for using such medication
- Information on the event, including date and time of onset of symptoms, severity, resolution (if applicable), date of death or other outcome (as applicable)
- Relationship with study medication in the investigator's opinion

Toxic death should be reported immediately to the sponsor using the SAE Report Form. Also death as a result of progression of disease (no relatedness to study medication) needs to be reported using the SAE Report Form (option "not related" in the SAE reporting form section "relatedness to study medication"). A detailed description of the cause of death should be provided. Autopsy reports, if available, should also be sent to the sponsor as soon as they become available. Any additional information which becomes known to the investigator should be provided in a follow-up report. The severity of SAEs will be graded according to NCI-CTCAE 4.03 (see Section 8.3.2.3). SAEs must be followed up until a definite outcome can be documented, the event has resolved or stabilised, or the event is diagnosed as a chronic condition.

Also all pregnancy cases **must be reported within 24 hours on the corresponding Pregnancy Form**, once the investigator or other study site personnel are aware of the pregnancy.

The Sponsor is obliged to report SAEs and SUSARs to the respective authority within the statutory reporting period. The reporting is delegated by the sponsor to the Pharmacovigilance representative (see page 5).

#### **8.3.2.6 Additional Provisions due to the Nature of the Underlying Disease**

Progression-free interval is the primary endpoint of this study. Tumour progression will be considered **not** to be an SAE within the scope of this study. However, death or other serious adverse events linked to disease progression/tumour progression will be considered as SAEs. If these serious

adverse events are linked to the disease progression/tumour progression, a diligent evaluation of the IMP/RP impact (see Section 8.3.2.2) through the reporter is necessary before the relatedness is classified as “unlikely” or “not related”.

The SAE cases where the relatedness was classified as either “not related” or “unlikely” will be treated by the sponsor as not related to the IMP/RP and thus will not underlie the provisions of the expedited reporting of SUSARs (the latter does not affect the local provisions to submit local fatal SAEs if required and applicable).

The SAE cases where no relationship to the IMP/RP was stated will be treated as “possible” and a follow-up with the reporter will be initiated.

The SAE cases where the relationship was stated as “not assessable” will be treated as “unlikely” and a follow-up with the reporter will be initiated.

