### ***Drug treatment***

### ***Non-drug treatment***

### ***Causal relationship to study drug***

The assessment of a possible causal relationship between the AE and the administration of the study drug is based on the following question:

“Is there a reasonable likelihood that the event was caused by the study drug?”

Possible answers are:

- Related (plausible time relationship to the administration of IMP/RP. No plausible explanation by underlying/concurrent disease or other drugs/events),
- Possible (plausible time relationship to the administration of IMP/RP, but the AE can be also plausibly explained by the underlying/concurrent disease or other medicinal products/events),
- Unlikely (unlikely temporal relationship to the administration of IMP/RP. Other medicinal products, events, and the underlying/concurrent disease provide a plausible explanation)
- Not related (clear evidence that the AE is not connected to the IMP/RP administration)
- Not assessable (no evaluation possible based on present data, additional clarification and follow-up necessary)

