8.1 Adverse Events

Adverse events prior to the first treatment will be captured for all enrolled patients and reported separately from treatment emergent AEs (TEAEs), as baseline findings.

The number of event episode as well as the count and percentage of patients with at least one event will be determined by treatment arm. The analysis will be presented overall and by maximal severity grades.

This analysis will be tabulated for treatment emergent AEs (TEAEs), Adverse reactions (ARs = AEs at least possibly related to the study drug), Serious TEAEs (TESAEs), Serious ARs (SARs), SARs by possible cause of event, TEAEs by action taken on the study drug (change or discontinuation), TEAEs that led to premature study termination, and Fatal TEAEs.

AEs will also be tabulated according to the primary system organ class (SOC), preferred term (PT) and maximal severity. Patient-based count and percentages will be given by treatment arm for SOC followed by those for PT in descending order of the IMP arm.

In this analysis a patient with several events with identical SOC and PT will be counted only once at the maximal severity.

This analysis will be tabulated for TEAEs, ARs, SAEs, SARs, TEAEs by action taken on the study drug (change or discontinuation), TEAEs that led to premature study termination, and fatal TEAEs.

A summary will also be presented by SOC and PT such as mentioned above by treatment arm for all pooled severity grades and pooled grades 3 or 4 TEAEs and ARs.

If deemed appropriate other analysis, table and summaries can be presented to further explore the pattern of adverse events.

All AEs will be listed.

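### Protocol 8.3.2.6 handles serious events of unassessable causality as unlikely, contrary to its own causality categories and its rule for missing causality, and SAP 8.1 has no rule for them

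*Protocol*

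**What the plan says.** Protocol 8.3.2.2, under the causal relationship to study drug, offers five answers: related, possible, unlikely, not related and not assessable. Two of them matter here:

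- "Unlikely (unlikely temporal relationship to the administration of IMP/RP. Other medicinal products, events, and the underlying/concurrent disease provide a plausible explanation"
- "Not assessable (no evaluation possible based on present data, additional clarification and follow-up necessary"

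Protocol 8.3.2.6 then sets the sponsor's handling of SAE cases:

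- A case in the unlikely or the not related class counts for the sponsor as having no link to the drug, and so stays outside expedited SUSAR reporting.
- "The SAE cases where no relationship to the IMP/RP was stated will be treated as “possible", and the reporter is followed up.
- "The SAE cases where the relationship was stated as “not assessable” will be treated as “unlikely". The same sentence opens a follow-up with the reporter.

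For a product before approval, Protocol 8.3.2.4 calls a response an adverse drug reaction when a causal link is "at least a reasonable possibility, i.e., the relationship cannot be ruled out". A separate definition follows for marketed products.

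SAP 8.1 builds its adverse reaction (AR) and serious adverse reaction (SAR) tables on this definition: "ARs = AEs at least possibly related to the study drug". It does not mention the not assessable category.

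**The concern.** Causality can be unknown in two ways: the field is left blank, or the reporter records that no judgement is possible on the data so far. Protocol 8.3.2.6 sends the first to possible and the second to unlikely, and gives no reason for the difference. A site that writes nothing triggers the cautious rule, while a site that records its uncertainty triggers the permissive one.

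Two things are at stake. The first is expedited reporting: a serious, unexpected event whose cause is open is handled as unrelated while the default stands. The second is the relatedness tables in the study report. Any error there runs in one direction, because leaving open cases out can lower the AR and SAR counts but cannot raise them. Relatedness matters in this trial because Protocol 11.2 asks the safety board to look particularly for acute and delayed radiation effects on bone marrow and kidneys.

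**Working it through.** The documents give no counts of SAEs, SUSARs or not assessable cases, and the plan states no figure to reproduce. The check is a comparison of the rules.

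**Step 1. The two categories differ in kind.** Under Protocol 8.3.2.2, unlikely needs improbable timing and a plausible alternative cause. Not assessable means that neither has been established. Moving a case from the second to the first supplies a conclusion that the reporter said could not be reached. For SAEs linked to progression, 8.3.2.6 itself asks for a careful evaluation of the drug's role before a case is called unlikely or not related; the default gets to unlikely without one.

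**Step 2. Follow each recorded answer through the rules.**

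| Recorded causality of an SAE | Sponsor's handling, Protocol 8.3.2.6 | Open to expedited reporting if unexpected | In AR/SAR tables, SAP 8.1 |
|---|---|---|---|
| Related or possible | as recorded | yes | yes |
| Blank | possible, with follow-up | yes | no rule stated |
| Not assessable | unlikely, with follow-up | no | no, as written |
| Unlikely or not related | not related | no | no |

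The second and third rows describe the same state of knowledge and have opposite outcomes. Both carry a follow-up, so follow-up does not explain the difference.

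**Step 3. Compare with the reaction definition.** For 177Lu-edotreotide, the pre-approval wording in Protocol 8.3.2.4 counts a response when the link has not been excluded. A link that cannot be evaluated has not been excluded, so the default contradicts the definition. For everolimus, which is marketed, the separate definition applies. There the conflict rests on Steps 1 and 2 only.

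**Step 4. Separate the two mechanisms.** Protocol 8.3.2.6 governs the sponsor's handling of SAE cases, and SAP 8.1 does not cite it. Not assessable events are missing from the AR and SAR tables because of the SAP's own definition. That gap also covers non-serious events, which 8.3.2.6 does not address.

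**Step 5. Direction and scale.** Let *k* be the number of SAEs still not assessable at analysis. Each adds 0 instead of 1 to the related SAEs, so that count is short by *k*. Only cases that are also unexpected can affect SUSARs, so that shortfall is at most *k*. In the patient-level tables, with the planned 200 and 100 patients as approximate denominators, one affected patient not already counted moves an arm's SAR percentage by 1/200 = 0.5 points (177Lu-edotreotide) or 1/100 = 1.0 point (everolimus). The value of *k* is unknown. It is zero if no such cases arise, or if follow-up resolves them all.

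**The case against.** The strongest defence is that unlikely is only an interim label. Protocol 8.3.2.6 opens a follow-up in the same sentence, and 8.3.2.2 already says that clarification is needed, so the answer may change. This is right as far as it goes and should be read with the rule. It does not settle the matter: no deadline is set, nothing is said about cases that stay unresolved, and the opposite default for a blank field has the same follow-up.

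The second defence is that the events remain visible, and this stands. All SAEs go to the sponsor within 24 hours whatever their causality (Protocol 8.3.2.5). The safety board reviews SAEs and deaths without a causality filter (11.1.1 and 11.2). SAP 8.1 tabulates serious and fatal treatment-emergent events regardless of relation, SAP 8.2 lists deaths and AEs, and 8.3.2.6 keeps any local duty to submit fatal SAEs. These safeguards protect the total count and periodic review. They do not replace expedited reporting.

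A reader might also infer more than the documents support:

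- That SUSARs and serious reactions are in fact under-counted. This requires such cases to exist and to remain unresolved, or to be resolved too late; for SUSARs they must also be unexpected.
- That 8.3.2.6 causes the gap in the AR and SAR tables. The SAP's own definition does, and amending the protocol alone would not change the tables.
- That the pre-approval reaction definition condemns the rule in both arms. It applies directly only to 177Lu-edotreotide.

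**Conclusion.** The point holds as a contradiction within the protocol plus a separate omission in the SAP. The default in 8.3.2.6 conflicts with the category definitions in 8.3.2.2, with the adjoining rule for missing causality and, for the investigational product, with the reaction definition in 8.3.2.4. An unexpected SAE of open causality can miss expedited reporting as a result. Independently, not assessable events fall outside the AR and SAR tables as SAP 8.1 is written.

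The textual conflict is certain. Its numerical effect is unknown and may be zero, and no estimate is offered because the documents give neither the number of SAEs nor the share recorded as not assessable. The conclusion assumes that *treated as unlikely* carries the consequence that 8.3.2.6 attaches to unlikely cases; the section offers no other reading. Total SAE counts are unaffected, and no efficacy endpoint, test or sample size depends on this. It should be corrected.

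**What to change.** 1. In Protocol 8.3.2.6, give not assessable SAEs the same default as SAEs with no stated causality, namely possible, until follow-up with the reporter resolves them. Unresolved cases then stay on the cautious side, so the missing deadline matters less.
2. In SAP 8.1, state that events still not assessable at analysis count as at least possibly related in the AR and SAR tables. This has to be written separately because the SAP does not take over the protocol's rule.

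The cost is an amendment to each document, a few more expedited reports and slightly higher related-event counts. Treatment, endpoints, sample size and alpha do not change.

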### **8.3.3 Physical Examination**

A physical examination will be performed at each study visit from baseline visit(s) until end of study. It consists of general appearance, orientation to time, space and person, cardio-pulmonary auscultation, manual abdominal examination, and further investigation of any abnormal system, as appropriate.

Physical examination will be performed prior to dosing of study medication.

All pertinent findings will be recorded in the subject’s study records and transcribed to the appropriate pages of the CRF.

### **8.3.4 Vital Signs**

Body temperature, supine blood pressure and heart rate will be measured at baseline visit(s) and at each study visit.

Body temperature: The same location as for first measurement will be used throughout the entire study.

Supine blood pressure and heart rate: Both parameters will be measured on the non-dominant arm after 5 minutes of supine rest.

Vital signs will be measured for all subjects at the points of time given in [Table 1](#) and [Table 2](#).

Subjects randomised into the Lu-edotreotide group will have additional vital signs collected prior to Lu-edotreotide infusion, immediately after end of infusion (approx. 0.5 h) and at 6, 24, 48, 72-96 hours post start of infusion.

Locations of measurements and results will be recorded in the patient's file.

### 8.3.5 Clinical Laboratory Tests

Blood and urine samples for clinical laboratory parameters will be collected for all subjects at the points of time given in [Table 1](#) and [Table 2](#).

Laboratory assessments will be performed by the institutional or local laboratories. Because of the potential for radioactivity in some blood and urine samples, the local laboratory must adhere to their SOPs and/or any guidance and regulations for handling radioactive substances.

Lu-edotreotide arm ONLY: at study site wherever possible. If not logistically feasible, inter-visit lab samples can be taken by a medical general practitioner (GP) in the vicinity of the patient's home.

Samples will be tested for the following parameters:

Haematology: haemoglobin, haematocrit, mean corpuscular volume (MCV), mean corpuscular haemoglobin (MCH), white blood cell count (total and differential: leukocytes, neutrophils, eosinophils, basophils, lymphocytes, monocytes), red blood cells, platelets.

Biochemistry: sodium, potassium, chloride, calcium, glucose, creatinine, urea, albumin, total bilirubin, aspartate transaminase (AST), alanine transaminase (ALT), alkaline phosphatase (AP), gamma-glutamyl transferase (GGT), lipase, amylase, total protein.

Clotting parameters: prothrombin time (quick), reagent-independent prothrombin ratio (international normalised ratio; INR), activated partial thromboplastin time (aPTT).

Urinalysis (dipstick accepted): specific gravity, pH, protein, glucose, blood, leukocytes, ketones, nitrite, albumin, creatinine. Alpha-1-microglobulin will also be tested in urine but only in centres with adequate technical equipment and an established test method.

Tumour marker: Chromogranin-A, further markers (see Section [8.2.1.3](#)).

The investigator will sign each laboratory printout and assess clinical significance. Clinically significant values have to be highlighted as "c.s." (clinically significant). The printouts will be included in the patient's file.

